STUDY PROTOCOL

Title: Evaluation of the Effects of Dexamethasone-Enriched Platelet-Rich Fibrin on Postoperative Pain, Edema, and Trismus Following Impacted Mandibular Third Molar Surgery: A Randomized Split-Mouth Clinical Trial

Principal Investigator: [name] [name]

NCT Number: Not yet assigned.

Affiliation: Department of Oral and Maxillofacial Surgery, Sivas Cumhuriyet University, Faculty of Dentistry, Sivas, Turkey

Document Date: June 18, 2023

1. Background and Rationale

Impacted mandibular third molar surgery often results in postoperative pain, swelling, and trismus, negatively affecting patient recovery. Platelet-rich fibrin (PRF) has been used to improve healing and reduce complications. This study investigates the enhanced effects of PRF prepared from blood enriched with dexamethasone, a corticosteroid with anti-inflammatory properties.

2. Objectives

- **Primary Objective:** To assess the effect of dexamethasone-enriched PRF on postoperative pain after mandibular third molar extraction.
- **Secondary Objectives:** To evaluate effects on postoperative edema, trismus, and analgesic consumption.

3. Study Design

A randomized, controlled, double-blind, split-mouth clinical trial. Each patient will receive both interventions in contralateral extraction sites: standard PRF vs dexamethasone-enriched PRF.

4. Participants

Inclusion Criteria:

- Healthy adults aged 18–25 years
- Bilateral symmetrical impacted mandibular third molars requiring extraction
- No systemic disease
- Good oral hygiene
- Provided written informed consent

Exclusion Criteria:

- Systemic or immunological disorders
- Recent corticosteroid or anti-inflammatory use
- Pregnancy or lactation
- Allergies to study medication
- Poor oral hygiene or active oral infections
- Temporomandibular joint disorders affecting mouth opening

5. Interventions

- Control: PRF prepared from standard venous blood.
- Test: PRF prepared from venous blood mixed with 4 mg dexamethasone sodium phosphate prior to centrifugation.

6. Outcome Measures

- **Primary Outcome:** Postoperative pain measured by Visual Analog Scale (VAS) at 24, 48, and 72 hours.
- **Secondary Outcomes:** Edema, trismus, and analgesic consumption measured on postoperative days 1, 3, and 7.

7. Sample Size

Sixteen patients (32 extraction sites) based on power calculation.

8. Statistical Analysis

SPSS 22.0; Independent samples t-test or Mann–Whitney U test depending on data distribution. Significance threshold $p < 0.05$.

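### Section 8 plans only unpaired significance tests for a split-mouth trial and names no effect estimate or confidence interval, so a p-value from 16 pairs cannot separate no effect from too little precision

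*Combined protocol and SAP*

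**What the plan says.** Section 3 sets out a split-mouth design: "Each patient will receive both interventions in contralateral extraction sites: standard PRF vs dexamethasone-enriched PRF". The primary objective in Section 2 is "To assess the effect of dexamethasone-enriched PRF on postoperative pain after mandibular third molar extraction", and Section 6 defines the primary outcome as "Postoperative pain measured by Visual Analog Scale (VAS) at 24, 48, and 72 hours".

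Apart from naming the software, Section 8 has two elements: the choice of test, "Independent samples t-test or Mann–Whitney U test depending on data distribution", and the criterion, "Significance threshold $p < 0.05". Both tests are for independent groups. Neither Section 8 nor any other section names a treatment difference, a confidence interval or another measure of effect.

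Section 7 gives the size as "Sixteen patients (32 extraction sites) based on power calculation". It does not state the target difference, the SD, the power or the sidedness behind that number.

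**The concern.** There are two linked gaps. First, the tests ignore the pairing that the design creates. If the two sides of one patient are positively correlated, an unpaired analysis leaves between-patient variation in the error term and the comparison loses precision. Second, the only planned output is a p-value set against a threshold. On the Mann–Whitney branch the plan does not call for a difference in VAS units at all.

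With 16 pairs this matters for the primary objective. A non-significant result could mean little or no benefit, or a sizeable benefit estimated too imprecisely to show. A significant result would come with no planned statement of how small the benefit might be. Since Section 7 gives no target difference, there is also no stated benchmark against which to read a null result.

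**Working it through.** **Inputs from the documents.** 16 patients and 32 sites, hence 16 pairs (Sections 3 and 7); threshold 0.05 (Section 8).

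**Assumptions.** Two-sided testing, normal data, equal SD on the two sides, 16 complete pairs, and a within-patient correlation (rho) between 0 and 0.7. The documents give neither an SD nor the VAS range, so results are in units of SDd, the SD of the paired differences, and are not converted to VAS points.

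**The plan's own figure.** The 16 patients cannot be reproduced, because Section 7 gives none of the inputs.

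**Step 1: paired analysis.**
- Half-width of the 95% CI = t(0.975, 15)/√16 = 2.131/4 = 0.533 SDd.
- At p just above 0.05 the observed difference is about 0.533 SDd, so the interval runs from about 0 to 2 × 0.533 = 1.07 SDd.
- Power from the noncentral t distribution: 46.5% at a true 0.5 SDd, 80.1% at 0.75 SDd and 96.2% at 1.0 SDd. A true 0.5 SDd is therefore non-significant in 100 − 46.5 = 53.5% of trials, or about 54%.

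**Step 2: the planned unpaired t-test on the same 16 pairs.**
- Half-width in units of the single-side SD = t(0.975, 30) × √(2/16) = 2.042 × 0.3536 = 0.722 SD.
- SDd = SD × √(2(1 − rho)), so the half-width in SDd = 0.722/√(2(1 − rho)).
- The far limit of a just non-significant result is twice that. The limits take the sample SDs as equal to the true ones.
- The non-significance rates come from simulation (50,000 trials per setting); the paired row is from Step 1.

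| Analysis | rho | SDd/SD | Half-width (SDd) | Far limit (SDd) | True 0.5 SDd non-significant | True 1 SDd non-significant |
|---|---|---|---|---|---|---|
| Unpaired t | 0 | 1.414 | 0.511 | 1.02 | 51% | 3% |
| Unpaired t | 0.3 | 1.183 | 0.610 | 1.22 | 65% | 7% |
| Unpaired t | 0.5 | 1.000 | 0.722 | 1.44 | 79% | 15% |
| Unpaired t | 0.7 | 0.775 | 0.932 | 1.86 | 93% | 39% |
| Paired t | any | – | 0.533 | 1.07 | 54% | 4% |

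**Step 3: direction of the error.** With no true effect, the unpaired t-test was significant in 5.2%, 2.1%, 0.8% and 0.1% of simulated trials at rho 0, 0.3, 0.5 and 0.7. For positive correlation the mismatch costs power; it does not inflate false positives.

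**The case against.** The strongest reply is that Section 8 is a two-line summary. Silence on estimates is an omission and not a decision to withhold them, and assessing an effect can fairly mean testing whether one exists. That stands as far as it goes. The plan nevertheless commits to no estimate, which leaves the choice between mean and median, paired and unpaired, open until the data are in.

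It is also fair that the loss from the unpaired test depends on an unstated correlation. At rho = 0 the unpaired t-test does no worse than the paired one (51% against 54% non-significant at 0.5 SDd) because it has more degrees of freedom. The loss appears once the correlation is clearly positive.

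A reader might infer four stronger points that the documents do not support:
- *That a true difference of one SDd would probably be missed.* The 1.07 SDd is the far confidence limit of a borderline result. The largest observed difference that stays non-significant in a paired test is 0.53 SDd, and a true 1 SDd is detected with 96% power.
- *That the sponsor intends to report non-significance as no difference.* No section says how such a result will be worded. This is a risk that the plan leaves open.
- *That adding an interval cures the imprecision.* It displays it. Only pairing can narrow the interval, and only if the correlation is positive.
- *That 16 patients are too few.* Section 7 gives no target difference, so that cannot be judged.

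Finally, three intervals for one primary outcome leave multiplicity across 24, 48 and 72 hours unresolved. That is a separate matter.

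**Conclusion.** The concern holds in a limited form. Section 8 uses tests that do not match the split-mouth design and plans no effect estimate or interval. If the trial is analysed as pairs, a just non-significant result is compatible with up to about 1.07 SDd. As planned, the corresponding figure is 1.02 to 1.86 SDd, and a true 0.5 SDd effect goes undetected in about 51% to 93% of trials, against 54% with pairing.

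The paired figures rest on two-sided testing, normal differences and 16 complete pairs. The unpaired range also rests on the assumed correlation of 0 to 0.7, and it describes the t-test branch; the Mann–Whitney branch was not simulated. This is a gap in the analysis plan that should be closed, and it does not prevent the trial from running.

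**What to change.** In Section 8:

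1. Replace the independent-samples tests with a within-patient analysis.
2. For VAS at 24, 48 and 72 hours, report the mean paired difference (test minus control side) with its two-sided 95% CI. If a rank method is used, report the Hodges–Lehmann paired estimate with its CI. Give the paired p-value alongside.
3. Report edema, trismus and analgesic consumption in the same way.
4. State that a non-significant result will be interpreted from its interval and not taken as evidence of no effect. If the sponsor wants a formal rule for excluding a worthwhile benefit, it must name that difference before the data are seen; the documents do not supply one.

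The cost is a few lines of text, with no extra patients, visits or data. The drawback is that a null or borderline result will look less conclusive.
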